#### **Description of Study Intervention**

#### **Research Design and Methods:**

#### Research Subjects & Recruitment (Aims 1, 2, and 3)

Subjects: A total of 60 subjects will be recruited: 30 with cannabis use disorder (CUD) and 30 healthy controls (HC) who do not use cannabis. Each HC will be carefully matched to each CUD subject by age, sex, socioeconomic status, education, nicotine use, and other relevant variables. CUD subjects will undergo PET, an optional EEG, and cognitive testing at Day 0 and Day 28. HC will undergo these same measurements at Day 0 only. Some study participants will be also enrolled in HIC # 2000032181 ("SV2A Density Cannabis Use Disorder"), since that study has shared goals and study personnel with our study. We have staff that are common to both studies. If a subject is also enrolled in HIC# 2000032181, common procedures except for PET scanning will be performed once between the two studies (i.e., MRI and cannabis abstinence procedures will not be duplicated). Whichever study the subject first signs up for will be where the abstinence data will be tracked. The subject would sign a release of information to share the information with the other study.

Recruitment and Screening: Subjects will be recruited with clinicians at Yale and in the greater Connecticut community with whom we have a long history of successful collaboration, including long-standing relations with the Yale Psychiatric Hospital inpatient and outpatient services and mental health clinics in the Greater New Haven area, as well as through flyers, public advertisement (newspaper, radio, internet postings), social media, and word of mouth. Subjects will be appropriately compensated for their participation in the study and retained during the cannabis abstinence period using our validated contingency management paradigm.

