with event-related potentials (ERPs), and will be performed as described previously. Baseline normalized evoked/Induced power and Interelectrode Coherence (ITC; also termed phase locking factor) will be determined using a wavelet-based time-frequency spectrogram via Analyzer 2.0. EEG Source Analysis: Standardized Low Resolution Brain Electromagnetic Tomography (sLORETA): Based on the scalp-recorded electric potential distribution, standardized low resolution brain electromagnetic tomography (sLORETA) will be used to compute the cortical three-dimensional distribution of current density. This will allow us to examine mGluR5 availability in ROIs in relation to EEG sources. The particular form of standardization used in sLORETA endows the tomography with the property of exact localization to test point sources, yielding images of standardized current density with exact localization, albeit with low spatial resolution (i.e. neighboring neuronal sources will be highly correlated). 104,105 sLORETA is the method of choice since it has no localization bias even in the presence of measurement and biological noise. 104 Furthermore, sLORETA has been validated in several simultaneous EEG/fMRI studies,  and in an EEG localization study for epilepsy.  In the current implementation of sLORETA, computations will be made both in a realistic head model,  using the MNI152 template,  and using each subject's structural MRI, with the three-dimensional solution space restricted to cortical gray matter, as determined by the probabilistic Talairach atlas. The intracerebral volume is partitioned in 6239 voxels at 5 mm spatial resolution. C.2.d. EEG Paradigms: RAVLT Task: A modified computer version of the Rey Auditory Verbal Learning Test (RAVLT) similar to Babiloni et al. (2009) will be utilized. The RAVLT will be administered while EEG data are collected in three separate conditions. In the passive listening condition, subjects will passively listen to a list of 15 words (presented one at a time) six times in a row. In the memory encoding condition, subjects will be administered a list of 15 words played one at a time, five times, and will be told to try and remember the list and to repeat as many words as possible after each list. A sixth distractor list will also be administered after the primary list as in the standard RAVLT. The inclusion of separate passive listening (which is not part of the standard RAVLT) and memory/encoding conditions will be included in order to compare neural signatures for both basic linguistic processing and processes related to memory encoding. Twenty minutes after the end of the encoding phase, subjects will be asked to repeat as many words as they can from the original list of words (the free recall phase). EEG will not be collected during the free recall phase. Following free recall, subjects will engage in a computerized recognition condition of the RAVLT. Subjects will hear words from the (1) original memorized list, (2) the distractor list, and (3) novel words not heard that day. Subjects will respond with a three-choice button box to indicate from which list each word originated. Words in the recognition condition will be presented every 4 seconds. This EEG version of the RAVLT allows separate examinations of neural oscillations during passive listening, memory encoding, and recognition. In addition, the words will be post-hoc sorted based on correct performance to examine activity during encoding for words that were accurately recalled (the "subsequent memory effect"). LTP Task: We induce and measure LTP using EEG with repetitive sensory stimulation. 100 This paradigm has been shown to have the properties of LTP including (1) frequency dependency, (2) temporal stability, (3) input specificity, and (4) de-potentiation by low frequency stimulation.  Tone pips (tone frequency 1000 Hz, presented for 50 msec) will be used in all stages of the task (i.e., for baseline, tetanus, and post-tetanic recording). During the baseline recording, 120 tone pips will be

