# 6 - Study Intervention

#### 6.1 Study Intervention(s) Administration

#### **6.1.1 Study Intervention Description**

#### **Study Schedule:**

Day 0: CUD subjects and healthy controls (HC) undergo PET scanning, an optional EEG, and cognitive testing.

Days 1-27: CUD subjects abstain from cannabis use, aided by our validated contingency management strategy.

Day 28: CUD subjects who are abstinent from cannabis use undergo repeat PET scanning, an optional EEG, and cognitive testing.

**Study Procedures:** Eligible subjects will undergo an MRI scan for coregistration of PET data and for individualized source analysis of EEG. CUD subjects will be instructed not to use cannabis after midnight of Day 0, and last use of cannabis will be recorded. On Day 0, CUD subjects and HC will be scanned via PET, administered EEGs, and undergo cognitive testing. The same CUD subjects scanned on Day 0 will then be aided with cannabis abstinence and monitored over the next 4 weeks. Participants will be paid after completion of each of the study procedures they complete. Payments include \$450 for each PET scan, \$50 for each MRI scan, \$50 for each set of cognitive tests performed on or around Day 0 and 28, \$50 for each optional EEG, and up to \$1,100 if abstinence is successfully completed as confirmed by urine samples and report.

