On each of the scan days, CUD and controls subjects will also be administered neuropsychological tests from the CogState Cognitive Battery[123,124], which we previously showed to be sensitive to detecting cognitive deficits in mood disorders[125]: executive control (Groton Maze Learning task, GMLT; Set-Shifting task, SST and Go No-Go, GNG)[126-134] and working memory (One Back task, ONB, and Two Back task, TWB)[135-137]. Further, the battery has been well-validated (studies using CogState batteries have been published in over 100 peer-reviewed journals). Most important for the current study, this battery is ideal for within-subject designs (i.e., it was specifically developed for repeated administration with minimal practice or learning effects). Finally, the CogState has been shown to have high test-retest reliability, thorough coverage of cognitive domains, comparable alternative forms, strong internal consistency, is well established in the general population, and has proven tolerability and acceptability. The entire battery takes approximately 30 minutes. For mood assessment, the Hamilton Depression Rating Scale (HAM-D) and Montgomery-Asberg Depression Rating Scale (MADRS) will be administered by highly trained and reliable raters. These assessments will be administered at screening and at the time of PET scans.

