# 9 - Statistical Considerations

# 9.1 Statistical Hypotheses

Aim 1: To determine differences in fronto-limbic mGluR5 availability between people with cannabis use disorder (CUD; n = 30) and healthy controls (HC; n = 30). Subjects will undergo [18F]FPEB PET neuroimaging to determine mGluR5 availability. Hypothesis 1: Frontolimbic mGluR5 availability will be higher in individuals with CUD compared with HC. Aim 2: Within CUD subjects, to examine the associations between mGluR5 availability and: (a) CUD severity; (b) impulsivity; (c) EEG; and (d) neurocognition. CUD severity and impulsivity will be determined by validated instruments. EEG outcomes (e.g., theta power, LTP) known to be sensitive to both cannabis and glutamate will be collected during tasks of verbal memory and neural plasticity (long term potentiation; LTP). Hypothesis 2: Higher mGluR5 availability will be associated with: (a) greater CUD severity (by DSM-5); (b) higher impulsivity; (c) lower theta-band power and LTP, and (d) worse performance on verbal memory. Aim 3: Within CUD subjects, to determine changes in mGluR5 availability, EEG, and neurocognition following cannabis abstinence. CUD subjects from Aim 1 will repeat PET scanning, EEG, and cognitive testing following a 28-day period of confirmed abstinence aided by contingency management. Hypothesis 3: Following cannabis abstinence: (a) mGluR5 will decrease; (b) theta power/LTP will be increased; (c) memory will improve.

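### Hypothesis 2(d) concerns verbal memory, but the only verbal-memory test sits inside the optional EEG session and Section 9.2 tests working memory instead

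*Combined protocol and SAP*

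**What the plan says.** **Hypothesis.** Section 9.1 ends Hypothesis 2 with "c) lower theta-band power and LTP, and (d) worse performance on verbal memory". The Synopsis, Section 3.1 and the opening of the Aim 2 text in Section 9.2 say the same. Hypothesis 3 is worded more broadly: "b) theta power/LTP will be increased; (c) memory will improve".

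**Where verbal memory is measured.** The RAVLT appears only in the Synopsis under C.2.d, EEG Paradigms: "The RAVLT will be administered while EEG data are collected in three separate conditions". The EEG conditions are passive listening, encoding and recognition. Delayed recall comes 20 minutes after encoding, and for that part "EEG will not be collected during the free recall phase".

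**Status of the EEG.** The Synopsis states: "CUD subjects will undergo PET, an optional EEG, and cognitive testing at Day 0 and Day 28". Section 6.1.1 says of Day 0: "CUD subjects and healthy controls (HC) undergo PET scanning, an optional EEG, and cognitive testing". It also pays for EEG ($50 each) separately from cognitive testing ($50 per set). Section 5.3 and the abstinence text of 6.1.1 mention the Day 28 EEG without the word optional, but do not withdraw the option.

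**Required cognitive session.** CogState is given on each scan day and is not labelled optional. Its tasks cover executive control and "working memory (One Back task, ONB, and Two Back task, TWB". No word-list or other verbal task is listed.

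**Schedule tables.** The Schedule of Activities and the Section 8.1 table source the Verbal Memory row to EEG theta power or coherence. Neither lists a recall score.

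**Analysis.** For Aim 2, Section 9.2 correlates mGluR5 with, among others, working memory performance, and takes negative correlations with it as support for Hypothesis 2. For Aim 3, model 3 tests cognition. Section 9.3 (analysis populations) is marked N/A.

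**The concern.** Two gaps meet at Hypothesis 2(d).

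The first is measurement. The outcome is a behavioural score, yet the only test that yields it is tied to a procedure that subjects may decline. Verbal-memory data would then come from a self-selected part of the CUD group. The replacement rule in Sections 6.1.1 and 6.4 covers dropouts, not EEG refusal, and the plan has no missing-data rule for this case.

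The second is analysis. The hypothesis names one construct and Section 9.2 tests another. A significant working-memory correlation would be reported as supporting Hypothesis 2 although the verbal-memory component had not been tested.

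The Aim 2 power statement assumes that all 30 CUD subjects contribute. A verbal-memory score not collected at Day 0 cannot be recovered later.

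**Working it through.** **Step 1. Match hypothesis, measure and analysis.**

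| Item | Memory construct | Instrument | Depends on EEG consent? |
|---|---|---|---|
| Hypothesis 2(d) (9.1) | Verbal memory | RAVLT (C.2.d) | Yes, as written |
| Schedule tables (Synopsis, 8.1) | Verbal memory as EEG theta | EEG | Yes |
| Aim 2 analysis (9.2) | Working memory | CogState One Back, Two Back | No |
| Hypothesis 3(c) (9.1) | Memory, type not stated | Not stated | Not determined |
| Aim 3 model 3 (9.2) | Cognition | Not stated; CogState can supply it | No, if CogState is used |

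The 2(d) outcome and the Aim 2 memory variable do not coincide.

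**Step 2. Reproduce the plan's minimum for Aim 2.** Inputs from Section 9.2: r = 0.55, two-sided alpha 0.05, power above 80%. With Fisher's z:

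n = ((z₀.₉₇₅ + z₀.₈₀) / atanh(r))² + 3 = ((1.960 + 0.842) / 0.6184)² + 3 = 23.53, rounded up to 24.

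This agrees with the stated n = 24.

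**Step 3. Margin for refusal.** With 30 CUD subjects, 30 − 24 = 6 may decline EEG before a RAVLT analysis drops below the plan's minimum.

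**Step 4. Power if verbal memory exists only in EEG acceptors.** Power = Φ(atanh(0.55) × √(n − 3) − 1.960). The documents give no EEG uptake, so the refusal rates are assumptions.

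| Assumed refusal | n | Power |
|---|---|---|
| 0% | 30 | 0.895 |
| 10% | 27 | 0.858 |
| 20% | 24 | 0.809 |
| 7 of 30 | 23 | 0.790 |
| 30% | 21 | 0.747 |
| 40% | 18 | 0.668 |
| 50% | 15 | 0.572 |

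Simulating the t-test of the correlation gives values slightly higher: about 0.83 at n = 24, 0.81 at n = 23, 0.79 at n = 22 and 0.60 at n = 15. On that basis power falls below 80% at 8 refusals rather than 7. The pattern is the same.

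**Step 5. Comparison.** A CogState working-memory outcome stays at n = 30 and power 0.895 whatever the EEG uptake. Any loss therefore falls on verbal memory, the construct that 2(d) names.

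**The case against.** The strongest reply is that the analysis as written does not depend on EEG uptake. Section 9.2 names working memory for Aim 2, and CogState supplies it for every CUD subject. This is correct, and it means no power loss can be claimed for the test as planned. It does not rescue 2(d), because the stated outcome is then simply not tested. Section 9.2 also allows secondary or exploratory correlations with other domains. Verbal memory could enter there, but only for EEG acceptors and not as the planned test.

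A reader might infer that EEG decliners lose every memory outcome. The documents do not support this, since One Back and Two Back are given on each scan day without EEG.

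A reader might also infer that the Day 0 to Day 28 memory change in 3(c) requires EEG consent at both visits. That does not follow. Hypothesis 3(c) says only memory, and its model tests cognition, which CogState can supply. It would follow only if the sponsor chose RAVLT change as the 3(c) measure.

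Placing the RAVLT within the EEG session does have a purpose: comparing neural signatures across conditions and examining the subsequent memory effect. That justifies recording EEG during the test. It does not justify withholding the test from those who decline, particularly as delayed recall is done without EEG.

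Finally, uptake may be high. Up to 20% refusal still leaves n = 24.

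**Conclusion.** The point holds for Hypothesis 2(d). As written, EEG decliners give no verbal-memory score, no recall score is scheduled for anyone, and the planned Aim 2 analysis tests a different construct. This inconsistency rests on the text alone and needs no assumption.

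The size of the power loss is conditional. It arises only if RAVLT recall is the intended 2(d) outcome, and it depends on an uptake that the documents do not give. Under the plan's r = 0.55 and two-sided 0.05, Fisher-z power runs from 0.90 with no refusals to 0.57 at 50% refusal, and more than 6 refusals breach the stated minimum. The possible selection among EEG acceptors comes on top of this and cannot be quantified from the documents.

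The change is worth making before further Day 0 sessions are run. For 3(c), the only conclusion is that the memory measure should be named.

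**What to change.** 1. Give the RAVLT, in the same sequence, to all subjects in the required cognitive session (CUD at Day 0 and Day 28, controls at Day 0). Record EEG during it only in those who opt in.
2. Add a RAVLT recall row to the Schedule of Activities and the Section 8.1 table, separate from the EEG theta row.
3. In Section 9.2, name RAVLT recall as the 2(d) outcome and keep working memory as a separate measure.
4. State which memory measure tests 3(c). If RAVLT change is used, specify alternate word lists at Day 28 to limit practice effects.
5. Record whether EEG was running during each RAVLT, so that scores with and without EEG can be compared.

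If the sponsor instead intends working memory, Hypothesis 2(d) should be reworded to say so. The verbal-memory question then becomes exploratory.

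The cost is protocol wording plus extra test time for EEG decliners only. The instrument is already in the protocol. The protocol gives no total duration for the task, only the 20-minute delay before free recall, so the added time has to be estimated by the site.

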#### **Endpoints**

The primary endpoint is mGluR5 availability, as measured by FPEB, in cannabis-maintained and abstinent states.

Secondary endpoints are EEG outcomes and cognitive performance.

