
presented with a variable inter-stimulus interval between 1800 — 2600 msec. After the baseline recording, LTP will be induced using auditory tetanus. The tetanus will consist of two minutes of the tone pips presented at 13 Hz. Subsequently, the test phase will commence, which will consist of another presentation of 120 tone pips as in the baseline period. The primary outcome measure will be N100-P200 amplitude after the auditory tetanus versus before the tetanus. The N100-P200 complex will be determined via automated algorithms and verified manually as described previously. 112

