#### Schema

#### Schedule of Activities (SoA)

OUTCOMES	SOURCE/MEASURE	нс	CUD (baseline) Day 0	CUD (abstinence) Day 28
Neural Recepto	ors			
mGluR5 Availability	PET ROI's $V_T$ : OFC, anterior cingulate, vmPFC, dlPFC, hippocampus, amygdala	X	X	X
Cannabis Use Disorder — Clinically Relevant Functional Measurements				
CUD Severity	DSM-5		X	
Cannabis Use Patterns	Timeline Follow Back		X	X
Cannabis Withdrawal Severity	Cannabis Withdrawal Scale		X	X
Cannabis Craving	7-point Scale		X	X
Cannabis- Related Problems	Marijuana Problems Scale		X	
Impulsivity	BIS/BAS	X	X	

Reward Processing	Probabilistic Reward Task	X	X	X
Mood	HAM-D, MADRS, Visual Analog Scale for Mood States	X	X	X
Sleep	Pittsburgh Sleep Quality Index	X	X	X
Cannabis Biomarkers				
Cannabis Use Status	Urinary THC-COOH*	X	X	X
Neural Function				
Verbal Memory	EEG: Theta band power/coherence	X	X	X
Synaptic Plasticity / LTP	EEG: N100-P200 amplitude increase after auditory tetanus	X	X	X
Neurocognitive Function	CogState Cognitive Battery	X	X	X

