#### Protection against risk

- 1. Effective screening to exclude subjects who would be placed at a greater risk. This includes a medical history, the physical examination, and the screening studies (blood, urine and ECG) performed before starting studies. All screening procedures will be conducted by trained staff under the supervision of the PI. Screening procedures may take place under HIC# 2000032181, in which case they will not be repeated if the participant is also enrolled in that study and has signed a release of information.
- 2. The investigator or a person designated by the investigator will explain the benefits and risks of participation in the study to each subject. Subjects will then be asked to explain the study in their own words to ensure their understanding of the study procedures prior to obtaining informed consent.
- 3. To further prevent the risk of an adverse event and to minimize the harm incurred by such, all scans will be done in the presence of medical supervision and trained nursing

- staff at the Yale PET center. In the event of serious medical complications, the PET center has immediate access to or consultation with specialized medical units at the Yale-New Haven Hospital.
- 4. All subject information will be kept confidential and only members of the investigative team with appropriate IRB/HIC and HIPAA training will have access to the study data. Data will be maintained and secured in locked file cabinets or password protected electronic media. A numbering code will be used to assign a unique identifier to each subject. This information is available to study investigators and, in as far as the agents represent experimental pharmaceuticals, to representatives of the FDA and Nuclear Regulatory Commission for authorized inspection.

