# 6.3 Measures to Minimize Bias: Randomization and Blinding

N/A

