Aim 2: Within CUD subjects, to examine the associations between mGluR5 availability and: (a) CUD severity; (b) impulsivity; (c) EEG; and (d) neurocognition. Hypothesis 2: Higher mGluR5 availability will be associated with: (a) greater CUD severity (by DSM-5); (b) higher impulsivity; (c) lower theta-band power and LTP, and (d) worse performance on verbal memory. Power Calculations for Hypothesis 2: Using the same standards applied for hypothesis 1, we considered our preliminary data and conducted a literature review to determine what magnitude of correlation we could reasonably expect to see in this study between relevant variables of interest. We included studies with similar methodologies, which reported correlations between similar variables (i.e. similar EEG measures and cognitive/behavioral constructs, and an *in vivo* measurement of neuroreceptor or transporter availability in humans using PET). Examples include an unpublished study from our research group in which the correlation between mGluR5 availability and impulsivity in BPD and PTSD individuals ranged from 0.46. to 0.80 in frontal and limbic brain regions of interest (n= 56). Observed correlations ranged in magnitude from 0.21 to 0.80 (positive or negative) with a median r = 0.57. Magnitude of relevant correlations observed in our preliminary data are comparable (i.e., correlation between impulsivity and fronto-limbic mGluR5 availability, r = 0.896). We will evaluate aim 2 using correlational analyses. Using a correlation estimate of 0.55 (based on both review of the literature and our pilot data) and a two-tailed  $\alpha = 0.05$ , a priori power analysis suggested we will require a minimum n = 24 to achieve more than 80% power for the planned analysis. As we plan to conduct correlational analyses within the CUD group (n = 30), we will be adequately powered to test this hypothesis. Data Analysis for Hypothesis 2: Correlational analysis (Spearman or Pearson, as appropriate based on observed data distributions) will be used to test for associations between fronto-limbic mGluR5 availability, CUD severity, impulsivity,  $\theta$ - band power and LTP, and working memory performance. Multiple regression analyses will also be considered to control for potential confounding variables. a will be set at 0.05 for all planned correlational analyses. We will also assess for associations between mGluR5 availability and performance on

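### Section 6.3 marks blinding as not applicable, yet N100-P200 peaks are verified by hand with no masking to visit or tetanus block, which leaves Hypothesis 3(b) for LTP open to a small, avoidable scoring bias

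*Combined protocol and SAP*

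**What the plan says.** Section 6.3 carries the heading "Measures to Minimize Bias: Randomization and Blinding", and its whole content is N/A.

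The LTP task is described in the Synopsis under C.2.d, EEG Paradigms. The outcome is defined there: "The primary outcome measure will be N100-P200 amplitude after the auditory tetanus versus before the tetanus". The next sentence gives the scoring method: "The N100-P200 complex will be determined via automated algorithms and verified manually as described previously". The method thus has an automated pass followed by a human one. The text does not say what the human may change, or what that person knows about the recording.

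The Schedule of Activities lists "EEG: N100-P200 amplitude increase after auditory tetanus" for healthy controls, for CUD subjects at Day 0 and for CUD subjects at Day 28. The Synopsis sets the rank of these measures: "Secondary endpoints are EEG outcomes and cognitive performance". The study schedule makes the EEG optional at both visits.

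Two hypotheses give LTP a direction. For change after abstinence, section 9.1 predicts "b) theta power/LTP will be increased; (c) memory will improve". For association with higher mGluR5 within the CUD group, section 9.2 predicts "c) lower theta-band power and LTP, and (d) worse performance on verbal memory".

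The only coding of records appears under protection against risk (sections 2.3.3 and 8.2), as a confidentiality measure: "A numbering code will be used to assign a unique identifier to each subject". An identifier per subject does not hide the visit or the tetanus block.

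**The concern.** Randomization cannot apply to a comparison of CUD subjects with controls, or of Day 0 with Day 28. Masking of readers is a separate matter. It needs no randomization, and a single N/A covers both.

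Manual verification is the point at which a person can accept or alter the number that becomes the LTP outcome. If the file shows that it is a Day 28 recording taken after the tetanus, the reader knows which direction the study predicts. Aim 3 is a single-arm before-and-after comparison, so no concurrent abstinence control exists in which the same scoring habit would appear and cancel. What is at stake is false support for the LTP part of Hypothesis 3(b).

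**Working it through.** **1. Is any masking stated?** Section 6.3 says N/A. The LTP task text states a manual step and no masking. The identifier in sections 2.3.3 and 8.2 is per subject and serves confidentiality. The cited source for the verification method is not available here, so whether it includes masking is unknown; this protocol does not say so.

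**2. Which edits would bias Hypothesis 3(b)?** Treat LTP at a visit as a difference (an assumption, since the text says only after versus before):

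LTP(visit) = A(post, visit) − A(pre, visit)

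Change = LTP(Day 28) − LTP(Day 0)

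Let e be the mean scoring error in each cell. The bias in the change is

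[e(post, 28) − e(pre, 28)] − [e(post, 0) − e(pre, 0)].

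- An error common to both blocks of a visit cancels within that visit.
- An error common to both visits cancels between visits.
- Only an error that differs by block and visit together survives. Visit and block are therefore the two labels that matter most, and hiding either one from the reader makes such an error harder to produce.

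**3. Which planned comparisons use LTP?**

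| Comparison | Is LTP involved? | Label that could bias it |
|---|---|---|
| Aim 1, CUD versus HC | No, PET composite only | None |
| Hypothesis 2(c), within CUD | Yes, correlation with mGluR5 | The subject's own PET result |
| Hypothesis 3(b), Day 28 versus Day 0 | Yes, as a hypothesis | Visit with block |

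The data-analysis text for Aim 3 in section 9.2 specifies three repeated measures ANOVAs. The second names theta-band power and coherence and does not name LTP. The illustration below therefore assumes that LTP would be tested in the same way.

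**4. Illustration of size.** The plan has no figure to reproduce, because it gives no scoring error. Inputs:

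- n = 30 CUD subjects (section 9.2, Aim 3), and n = 20 as an assumed smaller number because the EEG is optional;
- two-sided α = 0.05;
- true change zero;
- assumed shift b = 0, 0.1, 0.2 or 0.3 SD of the paired change.

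With two time points, the repeated measures ANOVA is a paired t-test. False support for an increase is the upper-tail rejection probability

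P(T > t₀.₉₇₅), where T is noncentral t with n − 1 degrees of freedom and noncentrality b√n.

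The critical values are 2.045 (n = 30) and 2.093 (n = 20).

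| Assumed shift b | b√30 | Upper tail, n = 30 | b√20 | Upper tail, n = 20 |
|---|---|---|---|---|
| 0 | 0 | 2.5% | 0 | 2.5% |
| 0.1 | 0.548 | 7.6% | 0.447 | 6.2% |
| 0.2 | 1.095 | 18.4% | 0.894 | 13.4% |
| 0.3 | 1.643 | 35.5% | 1.342 | 24.7% |

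These figures show how sensitive a paired test is to a shift of a given size. They do not show that a shift of any size will occur.

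**The case against.** The case against giving this weight is substantial, and most of it stands.

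- Detection is automated first, so only the manual pass is exposed. EEG is secondary and optional. An N/A in a template section does not say that readers will be unmasked.
- A scoring error must differ by block and visit together to matter, as the algebra shows. Simple over- or under-reading cancels.
- The shift is assumed, n = 30 is not assured, and no Aim 3 model names LTP.

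A reader might also infer more than the documents support:

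- *That PET values and artifact rejection are equally exposed.* PET registration is algorithmic, regions come from an atlas, segmentation is by software, and EEG trials are rejected at a fixed ±100 µV. The MRI is said to guide region placement, but no manual PET or artifact check is described.
- *That knowing CUD from HC would bias a group result for LTP.* No such hypothesis or test is planned. Aim 1 is PET only.
- *That group or visit labels would bias Hypothesis 2(c).* This is a correlation among subjects who all have CUD. A reader would need each subject's mGluR5 value, and nothing says the reader has it.
- *That the bias could never be undone.* Verification is done on recorded data after an automated pass. If the automated values are kept, they can be compared with the verified ones, or the peaks can be scored again under masking.

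What survives is the unmasked manual step for Hypothesis 3(b). A predicted direction by visit, a human edit and no control arm are enough to justify a simple safeguard.

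**Conclusion.** The point holds in a narrow form. The protocol has a manual scoring step for LTP, states no masking of that step to visit or tetanus block, and marks its bias-control section N/A. Hypothesis 3(b) is the one planned comparison that visit and block labels could bias. The size cannot be derived from the documents. The rates of about 8%, 18% and 36% at n = 30 (6%, 13% and 25% at n = 20) rest on an assumed shift, on an assumed paired test of LTP, and on how many subjects accept the EEG.

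The primary PET endpoint, the group comparison and the within-CUD correlation are not shown to be affected. This is a minor point, worth acting on because the remedy is cheap.

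**What to change.** Replace N/A in section 6.3 with wording such as:

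> Randomization does not apply. Manual N100-P200 verification is done on files relabelled with a random code that hides visit, tetanus block and group, by an existing team member without access to that subject's PET or CUD-severity results. The automated values are kept, every override is logged, and codes are broken only after the values are locked.

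Add a cross-reference in the LTP task description. Hiding visit and block protects Hypothesis 3(b). Withholding PET and severity results is a precaution for Hypothesis 2(c). Keeping the automated values and the override log lets the effect of manual editing be checked afterwards.

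The cost is a relabelling script, a key holder from existing staff who does not do the verification, and a slight delay before data can be inspected by visit or group. Sample size, visits and recording procedures do not change.
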